3.1 Study Rationale

Study CGAR is a Phase 3b study to assess the long-term safety and tolerability of galcanezumab 300 mg in patients with episodic or chronic cluster headache who have completed one of the Phase 3 double-blind, placebo-controlled studies, CGAL or CGAM.

Study CGAR will implement a dosing strategy to more closely approximate what may occur in clinical practice. For each patient, the study investigator will determine whether or not to dose galcanezumab 300 mg at each monthly interval based on clinical symptoms and response.

Dosing will be no more frequent than once per month, and the investigator may choose to not dose galcanezumab for 1 or more months at their clinical discretion based on clinical efficacy.

As such, some patients may receive monthly long-term treatment with galcanezumab for a period of months or years during the study, while others may have 1 or more months of galcanezumab dose-free intervals based on the investigator's judgment of clinical efficacy. ~~If, however, the investigator stops monthly dosing due to safety concerns, dosing with galcanezumab should not be resumed.~~

5.1 Overall Design

Study Phase II: SP II is the single-arm open-label treatment phase during which patients can receive galcanezumab 300 mg administered SC up to once a month. If a patient meets all eligibility requirements, a urine pregnancy screen will be conducted at the first dosing visit, prior to dosing to confirm that a female patient is not pregnant before administering investigational product. Following the first dose of galcanezumab, the patient should remain in the office for 30 minutes of observation. The site will have a scheduled telephone visit (V23) with the patient approximately 1 week after the first investigational product administration to collect spontaneously reported AEs.

Every month, the decision whether to administer a monthly dose will be based upon the study investigator's judgment, which is not limited to, but includes assessment of the patient's clinical symptoms and response as follows:

- Dosing is up to once monthly; more frequent dosing is not allowed. The full 300 mg dose is to be administered, changing the dose amount is not allowed.
- If the patient remits and dosing is halted, the patient may remain in the study, but they should have an office visit 1 month after the last dose to complete the procedures listed in Event List F (Table 2.1). Dosing in this scenario may be re-initiated at the study investigator's discretion.

- Monthly telephone visits should be completed for patients who are not being dosed, but remain in the study (e.g., in remission).
- ~~Dosing may be re-initiated at the study investigator's discretion, as long as dosing was not halted due to a safety concern, and should be based upon the patient experiencing a cluster headache attack or the anticipated onset of a cluster headache period/bout, based on the patient's history (for example, the anticipated onset of a new cluster period in the spring based on a patient's history of spring-onset cluster periods).~~ If dosing is temporarily interrupted due to a potential safety concern, dosing may be re-initiated at the study investigator's discretion following a discussion and agreement between the study investigator and Lilly Medical that re-initiation of dosing is appropriate.
 - At the office visit **prior to re-initiation of dosing** the following procedures: ECG, immunogenicity, pharmacokinetics (PK), hematology, clinical chemistry, HbA1c and urine pregnancy are to be collected. The urine pregnancy must be negative and the ECG should be evaluated for safety prior to dosing.
- ~~**If dosing is halted for a safety reason, the patient should be discontinued (Section 8.2):**~~

6.1 Inclusion Criteria

1. Patients who **participated in and completed** either Study CGAL or Study CGAM. A study completer is defined as follows:
 - a. Study CGAL: a patient who has completed the double-blind treatment and post-treatment follow-up phases.
 - b. Study CGAM: a patient who has completed the double-blind treatment, open-label extension and post-treatment follow-up phases. However, if a patient entered Study CGAM prior to Study CGAR being open for enrollment, they will be considered a completer if they completed the double-blind treatment and post-treatment follow-up phases (e.g., opted not to participate in the open-label extension).

6.2 Exclusion Criteria

8. Use of therapeutic antibodies (except galcanezumab) during the course of the study (~~for example,~~ adalimumab, infliximab, trastuzumab, bevacizumab, etc.). Prior use of other therapeutic antibodies is allowed if an adequate washout has occurred (≥ 5 half-lives) prior to V2.
14. Any of the following cardiovascular-related conditions are exclusionary:
 - a. Since enrolling in Study CGAL or Study CGAM or prior to V2 (enrollment), have ECGs showing acute abnormalities of:
 - i. evidence of delayed ventricular repolarization including but not limited to a corrected QT (Fridericia's QT interval [QTcF]) interval >470 msec for women and >450 for men, **and/or**

- ii. evidence of atrioventricular (AV) depolarization of PR>220, or conduction delay of QRS>120, **and/or**
- iii. evidence of ischemia or any of the qualitative findings indicative of ST or J-point elevation, excluding those findings consistent with early repolarization (non-ischemic).

NOTE: Patients who meet 1 of the 14(a) ECG criteria during Study CGAL or Study CGAM may enroll in Study CGAR if the study investigator deems the finding not clinically significant.

- b. History of myocardial infarction (MI), unstable angina (UA), percutaneous coronary intervention, coronary artery bypass graft, deep vein thrombosis/pulmonary embolism since enrolling in Study CGAL or Study CGAM and prior to V2 of Study CGAR, or have planned cardiovascular surgery or percutaneous coronary angioplasty or surgery for peripheral arterial disease.
- c. Any lifetime history of vasospastic angina or stroke, or history of emergency room visit for chest pain in which an ischemic or cardiac event was not ruled out since enrolling in Study CGAL or Study CGAM and prior to V2 of Study CGAR.
- d. Clinical evidence of peripheral vascular disease (e.g., Buerger's Disease) or a diagnosis of Raynaud's Disease or Raynaud's Phenomenon.
- e. Have any history of intracranial or carotid aneurysm, intracranial hemorrhage, or stroke. ~~intra~~ ~~cranial~~ ~~tumors~~ ~~or~~ ~~significant~~ ~~head~~ ~~trauma.~~
- f. Have uncontrolled high blood pressure characterized by systolic blood pressure >160 mmHg or diastolic blood pressure >100 mmHg on 2 or more blood pressure assessments prior to V2 of Study CGAR.

NOTE: Patients who meet the 14(f) blood pressure criteria during Study CGAL or Study CGAM may enroll in Study CGAR if the study investigator deems the finding not clinically significant.

15. Any of the following medical conditions are exclusionary:

- a. Have a lifetime history of seizures (except for childhood febrile seizures).
- b. Have a history or presence of any other medical illness including but not limited to any cardiovascular, hepatic, respiratory, hematological, endocrine, psychiatric or neurological disease, or any clinically significant laboratory abnormality, that in the judgment of the investigator indicates a medical problem that would preclude study participation.
- c. Prior to V2, patients who have an elevation of $\geq 2 \times$ the upper limit of normal (ULN) for alanine aminotransferase (ALT), or $\geq 1.5 \times$ ULN for total bilirubin (TBL) or alkaline phosphatase (ALP) may be retested. The patient's results must be discussed with Lilly Medical and judged not clinically significant prior to enrollment.

NOTE: Patients with TBL $\geq 1.5 \times$ ULN are not excluded if they meet all of the following criteria for Gilbert syndrome:

1. Bilirubin is predominantly indirect (unconjugated) at screening (direct bilirubin within normal limits)
 2. Absence of liver disease
 3. ALT, aspartate aminotransferase (AST), and ALP $\leq 1 \times$ ULN at screening
 4. Hemoglobin not significantly decreased at screening
- d. Patients with a history of an intracranial tumor or head trauma must be discussed and judged not to indicate a medical problem that would preclude study participation by Lilly Medical prior to enrollment.

6.4 Screen Failures

Exclusion Criteria 16(b): If a patient fails eligibility due to a positive UDS, the patient may be considered for rescreen.

8.1.1 Temporary Discontinuation from Study Treatment

This protocol allows for temporary interruption of treatment, based on clinical symptoms of efficacy and response as judged by the investigator (Section 5.1). Dosing in this scenario may be re-initiated at the study investigator's discretion. Temporary discontinuation of treatment due to safety concerns or AEs is not allowed; discontinuation of treatment due to safety concerns or AEs will be considered permanent discontinuation of treatment and the patient must not be subsequently re-started on investigational product (Section 8.2). If dosing is temporarily interrupted due to a potential safety concern, dosing may be re-initiated at the study investigator's discretion following a discussion and agreement between the study investigator and Lilly Medical that re-initiation of dosing is appropriate.

Leo Document ID = 4f9bd8fd-7a4f-4a7c-bdbd-f7ae22950e0e

Approver: PPD
Approval Date & Time: 11-May-2017 20:13:36 GMT
Signature meaning: Approved

Approver: PPD
Approval Date & Time: 15-May-2017 14:56:33 GMT
Signature meaning: Approved

5.6. Handling of Dropouts or Missing Data	9
5.7. Multicenter Studies	9
5.8. Patient Disposition	9
5.9. Important Protocol Deviations.....	9
5.10. Patient Characteristics	9
5.11. Treatment Exposure and Compliance	10
5.12. Concomitant Therapy.....	10
5.13. Efficacy Analyses	10
5.14. Health Outcomes/Quality-of-Life Analyses	10
5.15. Bioanalytical and Pharmacokinetic/Pharmacodynamic Methods.....	11
5.16. Safety Analyses.....	11
5.16.1. Treatment-Emergent Adverse Events	12
5.16.2. Potential Hypersensitivity Events	12
5.16.3. Adverse Events Related to Injection Sites	13
5.16.4. Upper Respiratory Tract Infections.....	13
5.16.5. Suicide-Related Thoughts and Behaviors	13
5.16.6. Vital Signs and Weight	14
5.16.7. Electrocardiogram Intervals and Heart Rate	16
5.16.8. Laboratory Tests	17
5.16.9. Immunogenicity	17

- 5.16.9.1. Definitions of Patient ADA Status 18
- 5.16.9.2. Immunogenicity Analyses to be Performed..... 18
- 5.17. Reports to Be Generated at Each Interim and Final Database Lock..... 18
 - 5.17.1. Report to Be Generated at Interim Database Locks..... 18
 - 5.17.2. Report to Be Generated at Final Database Lock..... 19
- 5.18. Clinical Trial Registry Analyses 19
- 6. Reference..... 20
- 7. Appendices 21

Table of Contents

Table	Page
Table CGAR.5.1. Categorical Changes of Interest in Vital Signs and Weight.....	15
Table CGAR.5.2. Criteria for Treatment-Emergent Changes in ECG Intervals and Heart Rate.....	16

3. Revision History

Statistical Analysis Plan (SAP) Version 1 was approved on 12 July 2016 prior to first patient visit.

Statistical Analysis Plan Version 2 was approved prior to the database lock for the interim analysis supporting cluster headache indication submission. The overall changes and rationale for the changes incorporated in Version 2 are as follows:

- LY2951742 was replaced by galcanezumab in the body of the SAP.
- Analysis populations are updated. Evaluable analysis set is renamed to GMB-treated population; continuous treatment exposure population set is removed.
- GMB-treated time and off-treatment time are defined, and the safety analyses will be performed during the GMB-treated time in addition to the whole open-label treatment phase including both GMB-treated time and off-treatment time.
- The list of protocol deviations in Section 5.9 was moved to [Appendix 1](#) with a complete list of important protocol deviations.
- Safety analyses are reduced to summaries of AE overview, TEAE, SAE, and DCAE, since detailed planned analyses of Study CGAR safety data are more thoroughly described in PSAP for cluster headache indication in the context of combining the safety data from the originating studies with the safety data from Study CGAR.
- Section 5.17. Reports to Be Generated at Each Interim and Final Database Lock was added.
- Other minor corrections, modifications, and clarifications were made.

Statistical Analysis Plan Version 3 was approved prior to the final study database lock. The overall changes and rationale for the changes incorporated in Version 3 are as follows:

- General formatting and grammatical edits were made to improve clarity.
- The PGI-I analyses in Section 5.13 were updated to remove a graphical display; a tabular summary will be presented instead, without 95% confidence intervals.
- The description of the EQ-5D-5L questionnaire was updated in Section 5.14 to provide additional details for the derivation of the health state index scores. A description of the correlation analyses of EQ-5D-5L with PGI-I and cluster headache status was also added to meet the stated tertiary objectives.
- The following safety analysis descriptions were added in Section 5.16, to be consistent with the analysis approaches described in the SAPs for the other Emgality Phase 3 cluster headache studies:
 - Potential hypersensitivity events (Section 5.16.2)
 - AEs related to injection sites (Section 5.16.3)
 - Upper Respiratory Tract Infections (Section 5.16.4)
 - Suicide-related thoughts and behaviors (Section 5.16.5)
 - Vital signs and weight (Section 5.16.6)

- Electrocardiogram Intervals and Heart Rate (Section 5.16.7)
- Laboratory tests (Section 5.16.8)
- Immunogenicity (Section 5.16.9)
- The data cutoff dates for the two interim database locks were added in Section 5.17.1 for the interim locks used to support the regulatory submission and safety update report, respectively.
- The list of important protocol deviations in Appendix 1 were updated to align with the current version of the Trial Issue Management Plan (Version 12).

4. Study Objectives

4.1. Primary Objective

The primary objective of this study is to evaluate the safety of open-label galcanezumab within the context of expected medical practice in eligible patients with episodic or chronic cluster headache. Safety will be assessed using treatment-emergent adverse events (TEAEs), serious adverse events (SAEs), as well as suicidal ideation and behaviors utilizing the Columbia-Suicide Severity Rating Scale (C-SSRS).

4.2. Secondary Objectives

Characterize the reasons for discontinuation and frequency of adverse events (AEs) of interest for galcanezumab. The AEs of interest are those related to injection sites, hypersensitivity events, and upper respiratory tract infections.

Characterize the immunogenicity of galcanezumab. The immunogenicity will be assessed by the assessment of anti-drug antibodies (ADA) to galcanezumab, their relationship with AEs, and neutralizing ADA to galcanezumab.

4.3. Tertiary Objectives

Evaluate the effectiveness of galcanezumab by the assessment of the proportion of patients reporting a score of 1 (“very much better”) or 2 (“much better”) on the Patient Global Impression of Improvement (PGI-I) 1 month after receiving their first dose.

Evaluate the effect of LY2951742 on health values by the analyses of the European Quality 5-Dimensions 5-levels (EQ-5D-5L) on (1) health state index values; (2) each dimension of the descriptive system and dichotomized level responses; (3) European Quality Visual Analogue Scale (EQ-VAS) current health score; and (4) correlations with PGI-I, cluster headache status.

5. A Priori Statistical Methods

5.1. Study Design

5.2. Determination of Sample Size

The sample size for this study is not based on statistical or power considerations. This is an open-label safety study for patients who previously enrolled in and completed studies CGAL or CGAM. Therefore, the sample size is determined by the number of patients completing studies CGAL and CGAM who choose to enroll in this study.

5.3. Randomization and Treatment Assignment

All patients will receive the same treatment: galcanezumab 300 mg (GMB 300mg). Every month, the decision whether to administer a monthly dose will be based upon the study investigator's judgment.

5.4. General Considerations

General aspects of statistical analyses are described below.

Unless otherwise specified, analyses will be conducted in the GMB-treated population, which includes all patients who are enrolled and receive at least 1 dose of study drug in Study CGAR, and analyses will be presented with 1 treatment arm. Safety analyses will be performed during the GMB-treated time and during the whole open-label treatment phase (SP II), which includes both GMB-treated time plus off-treatment time. GMB-treated time is composed of monthly dosing intervals, that is, the time from a GMB dose to the next monthly visit. The time between the first monthly visit that a dose is not administered and the dosing re-initiation visit is counted as off-treatment time. Baseline will be the time during SP I prior to receiving the first dose in this study. For safety analyses during the open-label treatment phase, any time after the first dose of GMB 300 mg will be considered as postbaseline period no matter if it is during an on-treatment or off-treatment month. For safety analyses during the GMB-treated time, only events that occurred during the GMB-treated time will be considered as postbaseline values.

Statistical analysis of this study will be the responsibility of Lilly or its designee. SAS[®] software will be used to perform most or all statistical analyses.

Any change to the data analysis methods described in the protocol will require an amendment ONLY if it changes a principal feature of the protocol. Any other change to the data analysis methods described in the protocol, and the justification for making the change, will be described in the SAP or clinical study report (CSR). Additional exploratory analyses of the data will be conducted as deemed appropriate.

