5.6. Handling of Dropouts or Missing Data

Last-observation-carried-forward (LOCF) will be used in handling of missing data when it is applicable. For those patients who are lost to follow-up, or who drop out of the study, the analyses will include all data up to the point of their last data collection.

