5.11. Treatment Exposure and Compliance

This open-label study dosing will be based upon the study investigator's judgment and there will not be any formal computation of treatment compliance. Total number of monthly doses administered will be summarized for the GMB-treated population. Treatment received will also be reported in an individual subject listing by providing the date, time, and the injection dose administered.

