5.16. Safety Analyses

For purposes of the cluster headache regulatory submission, analyses of Study CGAR safety data are more thoroughly assessed in the context of combining the safety data from the parent studies with the safety data from Study CGAR. The planned integrated analyses are described in separate documents. For the purpose of Study CGAR alone, the safety and tolerability of treatment will be summarized by the following:

- AEs
 - TEAEs
 - by PT
 - by PT nested within system organ class (SOC)
 - SAEs, by PT nested within SOC
 - AE leading to discontinuation, by PT nested within SOC
 - Potential hypersensitivity events

- AEs related to injection sites
- Suicide-related thoughts and behaviors
- Vital signs and weight
- ECGs
- Laboratory measurements
- Anti-drug antibodies (ADA) and neutralizing ADA (NAb)

Unless otherwise specified, safety analyses will be conducted for the GMB-treated population during GMB-treated time and GMB-treated time plus off-treatment time. Categorical safety analyses will include both scheduled and unscheduled visits.

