5.16.3. Adverse Events Related to Injection Sites

Adverse events related to injection sites will be defined using terms from the MedDRA High Level Term “Injection site reactions.”

The number and percentage of patients with TEAEs related to injection sites will be summarized using MedDRA PT. Events will be ordered by decreasing frequency of PT term.

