5.16.5. Suicide-Related Thoughts and Behaviors

Postbaseline suicidal ideation, suicidal behavior, and self-injurious behavior without suicidal intent, based on the C-SSRS, will be summarized for the GMB-treated population during GMB-treated time and GMB-treated time plus post-treatment time. In particular, for each of the following events, the number and percent of patients with the event will be enumerated: completed suicide, nonfatal suicide attempt, interrupted attempt, aborted attempt, preparatory acts or behavior, active suicidal ideation with specific plan and intent, active suicidal ideation with some intent to act without specific plan, active suicidal ideation with any methods (no plan) without intent to act, nonspecific active suicidal thoughts, wish to be dead, and self-injurious behavior without suicidal intent.

In addition, the number and percent of patients who experienced at least one of various composite measures will be presented and compared. These include suicidal behavior (completed suicide, non-fatal suicidal attempts, interrupted attempts, aborted attempts, and preparatory acts or behavior), suicidal ideation (active suicidal ideation with specific plan and intent, active suicidal ideation with some intent to act without specific plan, active suicidal ideation with any methods [no plan] without intent to act, non-specific active suicidal thoughts, and wish to be dead), and suicidal ideation or behavior.

Specifically, the following outcomes are C-SSRS categories and have binary responses (yes/no). The categories have been re-ordered from the actual scale to facilitate the definitions of the composite and comparative endpoints, and to enable clarity in the presentation of the results.

Category 1 – Wish to be Dead

Category 2 – Non-specific Active Suicidal Thoughts

Category 3 – Active Suicidal Ideation with Any Methods (Not Plan) without Intent to Act

Category 4 – Active Suicidal Ideation with Some Intent to Act, without Specific Plan

Category 5 – Active Suicidal Ideation with Specific Plan and Intent

Category 6 – Preparatory Acts or Behavior

Category 7 – Aborted Attempt

Category 8 – Interrupted Attempt

Category 9 – Actual Attempt (non-fatal)

Category 10 – Completed Suicide

Self-injurious behavior without suicidal intent is also a C-SSRS outcome (although not suicide-related) and has a binary response (yes/no).

Composite endpoints based on the above categories are defined below.

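### Stand-alone CGAR safety percentages mix event rate with length of follow-up, because off-treatment and total follow-up time are not summarised

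*SAP*

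**What the plan says.** **Windows.** SAP 5.4 sets the rule: "Safety analyses will be performed during the GMB-treated time and during the whole open-label treatment phase (SP II"). SAP 5.16 states that "safety analyses will be conducted for the GMB-treated population during GMB-treated time and GMB-treated time plus off-treatment time", so the second window contains the first. SAP 5.4 builds treated time from monthly dosing intervals, each running from a dose to the next monthly visit. For the rest, "The time between the first monthly visit that a dose is not administered and the dosing re-initiation visit is counted as off-treatment time". SAP 5.6 adds that for patients who drop out or are lost, "the analyses will include all data up to the point of their last data collection".

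**Measure.** SAP 5.16.3 is typical: "The number and percentage of patients with TEAEs related to injection sites will be summarized using MedDRA PT". Sections 5.16.2 and 5.16.5 to 5.16.8 also use numbers and percentages of patients. The registry output in SAP 5.18 adds participants at risk and event counts, without person-time.

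**Exposure.** SAP 5.11: "Total number of monthly doses administered will be summarized for the GMB-treated population", with a dated listing of doses by subject. SAP 5.17.1 names exposure as an interim topic but gives no measure. Protocol 10.3.2.1 reports extent of participation only for patients who discontinue.

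**Follow-up.** One dose admits a patient to the analysis set (Protocol 10.2). Treatment may last months or years, with dose-free intervals (Protocol 3.1). The study has no fixed end (Protocol 5.3). Adverse events are reported at cut-offs of 27 March 2018 and 4 September 2018 and again at final lock (SAP 5.17).

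**Scope.** SAP 5.16 says of the pooled work with the parent studies: "The planned integrated analyses are described in separate documents". The Revision History refers to a separate plan for the cluster headache indication.

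**The concern.** A percentage of patients with an event is a clear summary when everyone is observed for about the same time. Here one patient may contribute a month and another several years. The percentage then depends on how long people were watched as well as on how often events occur, and it grows from report to report at an unchanged rate.

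The nested windows add a second difficulty. A reader will see one percentage for treated time and a larger one for the whole of SP II. Without the amount of off-treatment time, the gap could reflect many events in little time or few events in much time.

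Safety under long, intermittent, investigator-decided dosing is the primary objective, so this affects how the main result is read.

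**Working it through.** The documents give no event rate, patient-years or sample size, so there is no planned figure to reproduce. The dates come from the SAP; every rate, entry pattern and dropout hazard below is an assumption.

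**1. Longest possible follow-up.** SAP Version 1 was approved on 12 July 2016, before the first patient visit. From that date:
- to 27 March 2018: 623 days, 20.5 months (1.706 years);
- to 4 September 2018: 784 days, 25.8 months (2.146 years);
- to 2 March 2021 (SAP approval stamp, a stand-in for the final data date): 1694 days, 55.7 months (4.638 years).

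**2. Same rate, different percentages.** Take L = 0.10 first events per year, dropout hazard d, h = L + d, entry uniform over E years from 12 July 2016, and a cut-off at T years. The expected share with an event is

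(L/h) × {1 − [exp(−h(T − E)) − exp(−hT)]/(hE)}.

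First cut-off, no dropout (T = E = 1.706): 1 − (1 − exp(−0.1706))/0.1706 = 8.1%.

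Second cut-off, no dropout (T = 2.146):
- entry stops at the first cut-off (E = 1.706): 1 − [exp(−0.0441) − exp(−0.2146)]/0.1706 = 12.0%;
- entry continues to the second (E = 2.146): 1 − (1 − exp(−0.2146))/0.2146 = 10.0%.

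| Date | d = 0, entry stops at first cut-off | d = 0, entry continues to second | d = 0.4, stops | d = 0.4, continues |
|---|---|---|---|---|
| 27 Mar 2018 | 8.1% | 8.1% | 6.5% | 6.5% |
| 4 Sep 2018 | 12.0% | 10.0% | 9.2% | 7.7% |
| 2 Mar 2021 | 31.4% | 29.9% | 16.9% | 16.5% |

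**3. What a rate column would show.** For 100 patients, no dropout and entry stopping at the first cut-off, time at risk to first event is 80.6, 120.3 and 314.3 patient-years. With the expected events rounded to 8, 12 and 31, the rates with exact Poisson 95% intervals are 9.9 (4.3 to 19.5), 10.0 (5.2 to 17.4) and 9.9 (6.7 to 14.0) per 100 patient-years. The rate stays put while the percentage roughly quadruples.

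**4. The gap between the windows.** Assume 1 year of treated time at 0.30 first events per year. The treated-time percentage is 1 − exp(−0.30) = 25.9%. If off-treatment rate times off-treatment duration is also 0.30, the whole-phase percentage is 1 − exp(−0.60) = 45.1%. That product arises from 0.60 per year over 0.5 year, 0.30 over 1 year, 0.15 over 2 years or 0.10 over 3 years. A sixfold range of off-treatment rates gives the same pair of planned percentages, and only the off-treatment duration tells them apart.

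**The case against.** The strongest case against is that this is a single-arm descriptive study, that the percentage with an event over observed follow-up is a valid summary, and that the fuller safety work lies in the integrated documents. Much of this stands, and it rules out several stronger readings that a reader might infer.

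- **That treated exposure is unmeasured.** It is not. Treated time consists of monthly dosing intervals, so total doses divided by 12 approximates treated patient-years. Off-treatment time is what lacks a stand-in.
- **That off-treatment events are left out.** They are included in the whole-phase output; they are just not shown separately.
- **That the plan compares on-drug with off-drug frequency, or CGAR adverse events with those of the parent studies.** Neither is a stated objective of the stand-alone outputs. The parent-study exposures in SAP 5.16.9.2 serve only to group patients for immunogenicity.
- **That the interim percentage must rise from 8.1% to 12.0%.** That requires entry to close at the first cut-off. The first lock is tied to completion of the parents' double-blind phase (SAP 5.17.1). Entry to CGAR also requires post-treatment follow-up and, for most Study CGAM patients, the open-label extension (Protocol 6.1), and patients in remission may delay screening (Protocol 5.1). Later entry is plausible, and the rise may be only to 10.0%.
- **That the sponsor has no exposure-adjusted analysis.** The integrated plan cannot be seen, so this cannot be said.

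Two textual matters are small. SAP 5.16.5 describes its windows as "during GMB-treated time and GMB-treated time plus post-treatment time" where 5.4 and 5.16 say off-treatment, which is an editorial slip. The end of treated time for a patient who leaves without the next monthly visit is unstated, but that is an edge case, which Appendix 1 lists as an important deviation.

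What the objection does not remove is that a descriptive percentage over unequal follow-up needs its time base reported. That person-time could be derived from collected dates makes the remedy cheap; it does not mean that a summary is planned.

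**Conclusion.** The point holds as a worthwhile, low-cost improvement to the stand-alone CGAR outputs. The planned percentages mix rate with duration, and the difference between the two windows cannot be interpreted without off-treatment time.

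The size is illustrative. At a constant 10 first events per 100 patient-years with uniform entry, the rise between the interim cut-offs is about 2 to 4 percentage points without dropout (8.1% to between 10.0% and 12.0%), and about 1 to 3 points with a dropout hazard of 0.4 per year (6.5% to between 7.7% and 9.2%). By 2 March 2021 it is about 16% to 17% with that dropout and 30% to 31% with none; the latter assumes complete retention for up to 4.6 years. Only the dates come from the documents. The percentages are not wrong, and nothing here shows that a safety signal would be missed.

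**What to change.** **SAP 5.11.** Summarise patient-years of GMB-treated time, off-treatment time and total SP II follow-up. Close treated time at the next monthly visit and off-treatment time at the re-initiation visit; if there is none, close either at last data collection.

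**SAP 5.16.** Keep the percentages. Beside them, for GMB-treated time and for the whole of SP II, add first events per 100 patient-years with exact Poisson 95% intervals for TEAEs, SAEs, AEs leading to discontinuation, likely hypersensitivity events and upper respiratory tract infections. Time at risk in a window ends at the first such event in it, or at the end of the window.

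**Footnotes.** State that undosed months rely on telephone visits, which affects the whole-SP II rate as well as any off-treatment rate. State also that a constant rate may not hold for hypersensitivity, where long follow-up can dilute early events.

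**Exceptions.** Report injection-site events per dose or within GMB-treated time. Keep C-SSRS results as percentages of evaluable patients, because the scale is completed only at office visits. Use the term off-treatment time in 5.16.5.

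**Cost.** SAP wording, one derived person-time dataset and extra tables; dose, visit and event dates are already collected. The downsides are more output, wide intervals for rare events and reliance on a roughly constant rate.
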